Assessment Notes/Important Information about the family:

Elevated PHQ9 score? Yes No PHQ9 Total Score: _____

Depression resources provided Crisis Help Card provided

Referral to doctor or home visitor

Assessor/Coach Initials: _____

Risk Identification:

ATQ question #6 endorsed I don't think I can go on

PHQ9 question #9 endorsed Thoughts that I would be better off dead, or of hurting myself

Self-Harm

No plan, no intent to harm self, identifies reasons to not harm self

Lacks clear plan, states would not carry it out, identifies reasons to not harm self*

Has clear plan, means to harm self, cannot identify reasons to stop from harming self*

EMS Called* Participant called GA Crisis Line*

Contacted PI*

Child Abuse/Neglect

RPNI Completed* Safety information provided

Mandated Report Made*

Intimate Partner Violence

EMS called* Safety information provided

Referral to doctor or home visitor

Other Harm _____

Other: _____ **None**

**Must record in AE/SAE Log (on Google docs)*

Consult Needed: Yes No Date/time supervisor was consulted: _____
if you identified any risk above, a consult is needed

Is this a possible AE or SAE? Yes No AE/SAE #: _____

Report of clinical issue being addressed (List each issue one at a time and how it was addressed):

Report of consultation (what information was given to supervisor, what action needs to be taken, how did participant respond, what intervention was implemented, etc.):

Supervisor Comments (follow up steps needed, additional information, etc.):

Assessor/Coach Signature

Date

Supervisor Signature

Date

When complete, scan and email to [name] for filing and circulation to project team

Assessment Data Checklist

ID#: _____

PRE

POST

Date: _____

Before you leave the home:

Sprint signal: Successful Unsuccessful/Ineligible N/A

Questionnaire: Part 1 Part 2 Checked for missing data

Observation data

ASRI: Followed up for any endorsed safety questions

Safety Monitoring Forms (only used for participants with potential safety concerns)

iPhone Customization Questionnaire

Changes in Contact Information _____

Best times for calling to schedule/confirm training visit _____

Initial and date when items are complete: Initials: _____ Date: _____

At the office:

Enter Assessment Information into Access Database (S: drive)

Update Matriculation Table (Google docs)

Assessment Summary & Risk Identification completed and signed

- Email to supervisor if there is a safety concern

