- Share "Crisis Help Card" and offer to sit with mom while she contacts the Georgia Crisis & Access Line [name]

- Document on the **Assessment Summary and Risk Identification** exactly what the concerns were, what you did, and the mom's responses. Do not include identifiers. Email to Clinical Supervisor and **notify by text that you have done so.**

- "From the results of our assessment it looks like you might be experiencing Depression. I am not a therapist and I can't diagnose but there are people out there who can help. I wonder if anyone has ever talked with you about Depression." [Pause and give mom a chance to comment if she wishes] Share "Postpartum Depression Facts & Stories" and encourage the person to share booklet with and talk to their doctor or their baby's doctor at the next well child visit.
- Document on the **Assessment Summary and Risk Identification** exactly what the concerns were, what you did, and the mom's responses. Do not include identifiers. Email Supervisor. If you don't receive a signature reply within 24 hours, text and call. File signed copy + all other documentation in mom's folder within 72 hrs.

V. Adverse Event Guidelines

MOM & BABY NET GUIDELINES FOR ADVERSE EVENTS AND SERIOUS ADVERSE EVENTS:

General Notes:

AEs and SAEs are events that occur during the course of the participant's involvement in the project; that is, between signing the consent form and before completion of the final assessment.

Each AE and SAE will be recorded in the Adverse Events log, which will be reviewed weekly during supervision. The log must be updated on a regular basis to ensure accurate recording of events. Coaches and Assessors will fill out a clinical case note form and have them signed off by a supervisor within 48 hours (in some cases, additional forms will be required). The information contained in the Clinical Case Note Form will be entered into the AE log.

A unique tracking number will be assigned to each AE and SAE for reporting purposes. The tracking system will identify if the incident is an AE or an SAE and the next chronologically assigned number. For example, when the first AE is reported, it will be identified by "AE-01." If the next incident reported is an SAE, it will be identified by "SAE-01." The next AE would be identified by "AE-02" and so on.

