Possible SAEs need to be reviewed immediately by the PI to determine if the event meets criteria for an SAE. If the event is determined to be an SAE a brief report needs to be written immediately and provided to the PI for review. This report needs to be provided to the NICHD project officer within 24 hours of our discovery of the event.

In cases where there appears to be overlap in criteria, such that an event could be classified as either an AE or an SAE, code and respond to it as an SAE.

Adverse Event Definition:

Adverse event (AE): Any unfavorable medical occurrence or change that may present itself during treatment or administration of an intervention and which may or may not have a causal relationship with the intervention.

Our definition of an AE will incorporate such non-medical occurrences as suicidal ideation, exacerbation of psychopathology, minor symptoms of withdrawal, harm to self or others, disclosure of HIV status, disclosure of a crime committed by juvenile, mandatory report of child abuse, change of home placement or guardianship, homelessness (e.g., runaway), incarceration, and other incidents similar in level of adversity.

The events listed in the above definition are not exhaustive. Other events resulting or having the potential to result in similar injury or distress should be recorded in consultation with the clinical supervisor or PI. Further elaboration of the definition is provided below.

1. **Events reflecting significant change in physical health** include illnesses or injury that either:
 - a. Interfere with usual functioning (e.g., absent from school or work); or
 - b. For which the subject receives medical treatment

These events do not include

- a. Pre-existing conditions unless they worsen during the study period
- b. Life-threatening illnesses (see SAE below)

Examples: Flu; Diagnosis of chronic disease; Broken limb; substance withdrawal; increase in frequency or intensity of asthma attacks

2. Events reflecting significant change in mental health include: onset or exacerbation of suicidal ideation/behavior or non-lethal self-harm; onset of disorder; significant worsening of disorder symptoms

These events do not include

- a. Pre-existing mental health conditions unless they worsen during the study period
- b. Behavior change that does not directly reflect on change in mental health
- c. Life-threatening suicide attempts or self-harm (see SAE below)

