3. Events occurring within the family that could reflect or result in physical or psychological harm include: incidents of domestic violence that don't result in severe injury; child abuse reports to or investigations by DHS Child Welfare; testifying about prior abuse; parental separation or divorce; change in home placement or guardianship; youth running away; harm by family member to self or other.
4. Other Events that may cause psychological or minor physical distress include: criminal investigation, arrest, or short-term incarceration; automobile or other accident that does not result in serious harm; assault that doesn't require medical attention; economic stressors such as loss of job or eviction.

Serious Adverse Events:

Serious adverse event (SAE): Any medical occurrence that results in death; is life-threatening; requires in-patient hospitalization; creates persistent or significant disability/incapacity, or congenital anomaly/birth defects. These events do not include pre-existing conditions unless they worsen significantly during the study period.

Other events resulting or having the potential to result in similar injury or distress should be recorded in consultation with the clinical supervisor or PI. Further elaboration of the definition is provided below.

1. Medical event/injury that results in death or is life threatening would include those which: require or extend in-patient hospitalization; create persistent or significant disability/incapacity; or result in birth defects or congenital anomaly.
2. Serious events reflecting mental health/substance use problems would include: suicide attempts; drug overdose necessitating medical treatment; serious symptoms of withdrawal; admission to residential treatment center.
3. Violence within or outside the family that has the potential for serious bodily harm would include: incidents of domestic or nonfamilial violence that include actual or perceived threat of loss of life (e.g., use of weapons, choking, rape) whether or not the incident requires hospitalization.
4. Events that result in significant family disruption due to external intervention would include: DHS child welfare placement of child outside the home due to risk of or substantiated abuse, neglect, or endangerment; extended incarceration.

VI. COVID Remote Procedures

MOM & BABY NET RCT REMOTE RECRUITMENT CALL

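### The risk form's mandatory-log marks do not follow the adverse event definition, so suicidal ideation and partner violence may be logged inconsistently

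*Protocol*

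**What the plan says.** **Definition (Protocol Section V, Adverse Event Guidelines).** The general statement is "Our definition of an AE will incorporate such non-medical occurrences as suicidal ideation". Item 2 elaborates it for mental health as "onset or exacerbation of suicidal ideation/behavior or non-lethal self-harm" and excludes "Pre-existing mental health conditions unless they worsen during the study period". Item 3 brings in partner violence: "Events occurring within the family that could reflect or result in physical or psychological harm include: incidents of domestic violence that" do not cause severe injury. The reporting window lies "between signing the consent form and before completion of the final assessment". The General Notes give the logging rule: "Each AE and SAE will be recorded in the Adverse Events log, which will be reviewed weekly during supervision".

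**Form (Protocol Section II, Assessment Summary & Risk Identification).** An asterisk marks the lines that must be logged; its footnote begins "Must record in AE/SAE Log (on Google docs". There are three graded self-harm lines. The lowest, "No plan, no intent to harm self, identifies reasons to not harm self", has no asterisk. The middle and highest lines have one. The two boxes for endorsing ATQ item 6 and PHQ-9 item 9 have none. Under partner violence, only the emergency-call line is marked; the lines for safety information and for referral are not.

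**Decision tree (Protocol Section IV).** The Lowest category covers two kinds of mother: one who shows signs of depression but denies any thoughts of self-harm, and one who has had thoughts, has no plan, would not act and can say why. The Medium category covers a mother who acknowledges thoughts, lacks a clear plan, would not act and can say why.

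**The concern.** The definition and the form sort cases on different axes. The definition asks whether something began or worsened during the study. For self-harm the form's asterisk asks how high the risk is now. A mother whose suicidal thoughts first appear after entry, without a plan, fits the definition but is recorded on a line with no logging instruction. The reverse can also happen: stable thoughts that predate entry fall outside the definition but must be logged if the middle line is ticked.

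At stake is the consistency of the adverse event record in a trial that enrols depressed mothers, where suicidal ideation is an event that readers will look for. If two staff members can treat the same case differently and both be following the manual, the count in the log is hard to interpret.

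**Working it through.** No arithmetic applies. The check sets the texts side by side.

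**1. Is a plan or intent needed for ideation to be an adverse event?** No. Neither the general statement nor item 2 in Section V sets such a threshold. Item 2 turns on onset or exacerbation.

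**2. Can the lowest form line hold real ideation?** Yes, through the second kind of mother in the Lowest category. It can also hold a mother who denies any thoughts, so a tick on that line does not by itself show whether ideation was present.

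**3. Are the categories distinct?** Not fully. A mother with thoughts and no plan at all, who would not act and gives reasons, fits Lowest as written. She also fits Medium, because having no plan is one way of lacking a clear one. The routing lines above the boxes send a mother with no plan to Lowest and a mother with a plan plus protections to Medium, yet the Medium box describes someone without a clear plan. On the form, one placement triggers mandatory logging and the other does not.

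**4. Does the reporting window include the first assessment?** Yes. Consent comes before the questionnaires in both the in-home and the remote procedures. Ideation found at the first assessment is therefore inside the window, and only the exclusion for pre-existing conditions keeps stable cases out.

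**5. Definition against form, case by case**

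| Case | Meets the Section V definition? | Mandatory-log mark? |
|---|---|---|
| New or worsened thoughts, no plan, lowest line ticked | Yes | No |
| New or worsened thoughts, middle or highest line ticked | Yes | Yes |
| Stable pre-existing thoughts, middle line ticked | No (item 2 exclusion) | Yes |
| Stable pre-existing thoughts, lowest line ticked | No | No |
| Item endorsed, thoughts of self-harm denied, lowest line ticked | Not as suicidal ideation | No |
| Partner violence without severe injury, no emergency call | Yes (item 3) | No |

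The mark and the definition disagree in the first, third and last rows.

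**6. Does anything prompt staff for the fact that the definition needs?** No. The decision-tree questions cover the content of the thoughts, method, access, place and what holds the mother back. Neither they nor the form ask whether the thoughts are new or worse.

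**7. Is the log step present wherever the form is used?** No. The in-home assessment procedure (Section II, After Home Visit) tells staff to add a possible event to the log. The otherwise parallel text for the training visit (Section III, After Home Visit) leaves that line out. The remote checklists for use immediately after the pre- and post-assessment calls (Section VI) list the risk form, the data checklist, the Access database and the matriculation table, with no log step.

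**The case against.** The strongest reply is that a missing asterisk is not an exemption, and this is right. The mark makes logging compulsory for some lines; no text says that the others stay out. Several routes do not depend on it:

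- The form requires a supervisor consult for any identified risk.
- The form asks separately whether the event is a possible AE or SAE.
- The in-home procedure sends possible events to the log.
- The General Notes in Section V require every adverse event to be logged, with weekly review and a clinical case note signed off by a supervisor.
- The remote procedures have the form emailed for consultation when self-harm is endorsed.

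It is also fair to say that the partner-violence lines record actions taken rather than severity, so they were not written to classify events.

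A reader might go further and infer that every low-risk endorsement of PHQ-9 item 9 or ATQ item 6 after baseline is lost. The documents do not support that. Endorsement is not the same as ideation: the ATQ item is about feeling unable to go on, staff then ask about actual thoughts of self-harm, and some mothers on the lowest line deny them. A mother whose thoughts are stable and pre-existing is properly left out.

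A reader might also infer that a safety comparison between arms becomes unreliable. The SAP plans no between-arm analysis of adverse events, one form serves both arms, and answers to the two items are held as survey data at pre- and post-assessment, so new endorsement can be examined by arm without the log.

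What survives is narrower. For unmarked lines, logging rests on the judgement of staff and supervisor; nothing prompts them for onset or worsening; and outside the in-home assessment procedure the explicit log step is missing.

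**Conclusion.** The inconsistency is in the text and should be corrected. The form's mandatory-log marks do not match the Section V definition for new or worsened ideation without a plan, for stable pre-existing ideation on the middle line, or for partner violence without an emergency call. The overlap of the Medium and Lowest categories adds to the uncertainty. The effect is that adverse events may be under-counted or inconsistently counted. The documents do not show that they will be under-counted, nor that any line is exempt.

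The size cannot be given: the documents state no rate of ideation or partner violence, no expected number of events and no split across the three self-harm lines. No planned outcome analysis changes.

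The conclusion rests on two readings. First, item 2 is taken to elaborate the general statement, so that onset or worsening is what counts. Second, stable ideation present before consent is taken to fall under the exclusion for pre-existing mental health conditions. If the second reading is wrong, the mismatch for stable ideation on the middle line disappears, but stable ideation on the unmarked lowest line would then become a further mismatch.

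**What to change.** - Reconcile the form in Section II, the decision tree in Section IV and the definition in Section V so that log entry follows the definition rather than the risk line. The sponsor should settle where Medium ends and Lowest begins, and record denial of any thoughts separately from thoughts without a plan.
- Add an item asking whether the event is new or worse since baseline to the self-harm and partner-violence sections of the form, and attach the log asterisk to it. State how the item is answered at the first assessment, which falls after consent and has no earlier form to compare with.
- Repeat the log step in the training-visit procedure and in the remote pre- and post-assessment checklists.

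This changes recording only; the response to a mother at any risk level stays as it is. The cost is one form edit, short additions to the checklists and somewhat different log counts: more entries for new low-risk ideation and non-severe partner violence, and fewer for stable pre-existing ideation.

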3. DETERMINE ELIGIBILITY

Now we need to make sure that you are eligible for the project. There are some requirements for participating. Before spending any more time explaining the program, I would like to ask you a few questions to find out if you can indeed participate in this study. Are you comfortable with that? Your answers will be kept strictly confidential.

Age:

- *Are you 18 years of age or older?*
 - If Yes, continue and record mom's birth date on the recruitment form.
 - If No, **ineligible**. Go to page 5.

Residency

- *Do you live in the metro Atlanta area and plan to stay here during the next year?*
 - If Yes, continue
 - If No, **ineligible**. Go to page 5.

Baby

- *How old is your baby?*
 - Ask mom baby's age and date of birth. Record on recruitment form.
 - If baby is younger than 12 months, continue.
 - If baby is older than 12 months, **ineligible**. Go to page 5.

Stressful Situations

Sometimes families are experiencing stressful situations in their lives that can make it hard for them to be a part of a study such as this, either because the situation makes it burdensome for the family to participate in the study and/or because the family may need help that cannot be provided within the study. I am going to read you a list of some situations that families experience that make it a good idea for them to NOT participate in this study for the reasons that I just mentioned. You don't have to tell me which of these situations apply to you if any do. When I finish reading the list, I'll ask if any of these situations describe you.

- 1) *You have been diagnosed with schizophrenia.*
- 2) *You have received treatment or medication to help with hallucinations or delusions such as seeing or hearing things other people can't see or hear or having ideas that others might think are odd or strange, like people are out to get you or trying to hurt you.*
- 3) *You are currently receiving inpatient substance abuse treatment.*
- 4) *You live in a homeless shelter or domestic violence shelter.*
- 5) *Your infant is currently in intensive treatment for a genetic or health condition.*
- 6) *You do not have permanent legal guardian custody of your infant.*

Again, you don't have to tell me which of those might apply to you. However, please think about the situations I just mentioned, and answer "yes" or "no." Do any of these situations apply to you?

- If YES, **ineligible**. Go to page 5.

- If NO, continue.

Depression Screening (only do if not already completed by referring provider; mark responses on PHQ2 form)

Lastly, since our program is for moms who have been bothered by feeling down, we want to see how you've been feeling over the past 2 weeks. I'm going to read 2 statements with some answer choices for each one.

Over the past 2 weeks, how often have you had little interest or pleasure in doing things? Not at all, several days, more than half the days, or nearly every day?

Over the past 2 weeks, how often have you felt down, depressed or hopeless? Not at all, several days, more than half the days, or nearly every day?

- If score is less than 3, **ineligible**. Go to page 5.
- If score is 3 or higher, continue.

- ❖ **If participant is Eligible and there is no waitlist, go to page 6**
- ❖ **If participant is Eligible and there IS a waitlist, go to page 8**

4. IF PARTICIPANT IS INELIGIBLE

Thank the Mom for her time and let her know that she is not eligible (choose the response below that best fits with why the participant is ineligible).

Thank you for taking the time to answer my questions. Unfortunately you are not eligible for the project at this time.

- **Age:** *The project requires that moms be at least 18 years of age*
- **Baby:** *The project requires that babies be younger than 12 months of age at the time we begin the first assessment.*
- **Residency:** *The project requires that moms must live in the metro Atlanta area and remain there for the next year.*
- **Stressful situations:** *We have found that participation in the study is very challenging for those that are dealing with other stressful situations in their life.*
- **Depression screening:** *Based on our brief screening, there are no signs that you are struggling with depression symptoms at this time. But we know these feelings can change. If anything changes we encourage you to follow up with your doctor and or local community program or reach back out to us in a few weeks.*

Update contact and eligibility information in Matriculation Table.

File recruitment form in ‘Not Enrolled’ folder (program coordinator’s office).

5. **PARTICIPANT IS ELIGIBLE – NO ACTIVE WAITLIST**

Based on the information you just gave me, you are eligible to participate in the program at this time.

What questions do you have right now? Answer any questions.

Schedule assessment call: *If you are interested in participating, the first step will be for us to complete the consent call. I will email you a copy of the project's consent form. This document will explain in detail the purpose of the Mom and Baby Net project, what you will be doing in the project, and how we will keep your information safe. We are taking necessary precautions to keep you, your family, and our staff healthy during the Coronavirus pandemic. The Pre-assessment and training calls will be conducted remotely using Zoom – an app that allows us to have a video call. I will later explain how Zoom works if you choose to participate. The iPhone agreement form will also be emailed to you. This document covers expectations of loaning you the iPhone to complete the Mom and Baby Net project. Your phone service will be covered while you are participating in the program. We will monitor your progress on a month to month basis. If you are making progress and staying in communication with your coach, we will renew your service for the next month. If we lose contact with you, or you are not making progress in the program, your phone service may be discontinued; If we cannot reach you and your phone is not returned, it will be reported as lost or stolen. I will also mail a copy of both of these forms to your home. Have you still been receiving mail and packages as usual during this time?*

I'd like to go ahead and set up a time for the first assessment call. It will take about 20 minutes.

- When scheduling the 1st call, it might be best to schedule this visit at a time of day when your baby is usually napping or can be watched by another adult in the home so you can focus on the information we will go over.*
- Let's schedule for 4-5 days from now to give time for the forms to arrive in the mail. When is good for you? Is there a day or time that works best for you? Do you prefer mornings or afternoon?*
 - Record the scheduled appointment time in the Access Database along with any notes*
 - Record appointment in the Mom & Baby Net Outlook calendar or other scheduling software*

Confirm all the contact and demographic information and edit if necessary in the database:

- NOTE:** Make sure to confirm if mailing address and physical address are different, confirm spelling of first and last name, and confirm date of birth and name of baby
- Is this the best number to call to follow-up with you?*
- Can we leave a message at this number? If it's a cell # - ask if you can text her appointment reminders.*
- If for some reason I can't get a hold of you, it would be helpful to have some contact names and numbers of people who would be able to reach you. Do you have one or two people who typically stay in touch with you and know how to locate you even if you move or change numbers? Can I get their names and phone numbers?*

- Record the contact names/numbers on the recruitment form

Recap:

- *I believe I have all the information I need. I'd like to quickly recap a couple of points*
 - I will email and mail you the consent form and iPhone agreement.
 - On our scheduled call, we will go over the forms and I will answer any questions you have. It will take about 20 minutes.
 - Then we will go over the next steps of sending the iPhone and setting up the next calls.
- *Do you have any questions about the project in general?*
 - If yes, try and answer any questions they have or let them know you will call back with the answer.
 - If no, continue.
- *Give us a call if you have any questions or concerns before your scheduled appointment. We will also give you a reminder call or text the day before your appointment.*
- *We really want to thank you for your interest in our study and being willing to let us come to your home during this busy time in your life. We look forward to meeting with you on _____ at _____ am/pm.*

❖ **CONTINUE TO 'AFTER THE INITIAL RECRUITMENT CALL' STEPS (page 9)**

6. **PARTICIPANT IS ELIGIBLE – WAITLIST**

Based on the information you just gave me, you are eligible to participate in the program at this time.

Explain Waitlist: *We currently have as many moms as we can take in the program right now but we will have openings soon. We estimate that you will be able to enroll in about [give approximate timeframe, i.e. 2 weeks, 1 month, etc.]. Since we already know you are eligible we will simply need to schedule the first **call** as soon as we have an opening. I will call back to schedule as soon as I know there's a spot. If I can't reach you within a week, I will have to move to the next person on the waitlist.*

What questions do you have right now? Answer any questions.

Let me confirm all of your contact information so we can be sure to reach you.

Confirm all the contact and demographic information. Unless they refuse, get at least 2 phone numbers:

- **NOTE:** Make sure to confirm if mailing address and physical address are different, confirm spelling of first and last name, and confirm date of birth and name of baby
- *Is this the best number to call to follow-up with you?*
- *Can we leave a message at this number? If it's a cell # - ask if you can text her appointment reminders.*
- *If for some reason I can't get a hold of you, it would be helpful to have some contact names and numbers of people who would be able to reach you. Do you have one or two people who typically stay in touch with you and know how to locate you even if you move or change numbers? Can I get their names and phone numbers?*
 - Record the contact names/numbers on the recruitment form

Recap:

- *I believe I have all the information I need.*
- *Give us a call if you have any questions or concerns before you hear from me again.*
- *We really want to thank you for your interest in our study and for your patience while we wait for a spot to open up.*

When you call mom back to schedule appointment, use scheduling script in section 5.

❖ CONTINUE TO ‘AFTER THE INITIAL RECRUITMENT CALL’ STEPS (page 9)

